10.4.2. Safety Analyses

All safety analyses will be performed on the Safety Population.

Adverse events (AEs) will be coded using the standard GSK dictionary, Medical Dictionary for Regulatory Activities (MedDRA), and grouped by body system. The number and percentage of subjects experiencing at least one AE of any type, AEs within each body system and AEs within each preferred term will be presented for each treatment group. Separate summaries will be provided for all AEs, drug related AEs, fatal AEs, non-fatal SAEs, AESIs and AEs leading to withdrawal.

Deaths and SAEs, if applicable, will be documented in case narrative format.

10.4.3. Other Analyses

Any other analyses will be described in the reporting and analysis plan

10.4.4. Interim Analyses

No interim analyses are planned.

The protocol consists of two sub-studies to assess the following treatment comparisons: ELLIPTA DPI (treatment option 1) versus the combination of DISKUS-HandiHaler (treatment option 2) in Sub-study 1 and ELLIPTA DPI (treatment option 1) versus the combination of Turbuhaler-HandiHaler (treatment option 3) in Sub-study 2.

Sub-study 1 will report out independently of Sub-study 2.

12. APPENDICES

12.1. Appendix 1: Abbreviations and Trademarks

Abbreviations

ASE	All Subjects Enrolled
COPD	Chronic Obstructive Pulmonary Disease
CONSORT	Consolidated Standards of Reporting Trials
CRF	Case Report Form
CV	Cardiovascular
DPI	Dry Powder Inhaler
HCP	Healthcare Professional
ICS	Inhaled Corticosteroids
IEC	Independent Ethics Committees
IRB	Institutional Review Boards
ITT	Intent-to-treat
IWRS	Interactive Web Response System
LABA	Long-Acting Beta2-Agonist
LAMA	Long-Acting Anticholinergic
MedRA	Medical Dictionary of Regulatory activities
PIL	Patient Instruction Leaflet
SABA	Short Acting Beta-Adrenergic Agonist
SAE	Serious Adverse Events
SAMA	Short Acting Muscarinic Antagonist
SRM	Study Reference Manual
SUSAR	Suspected Unexpected Serious Adverse Reactions

Trademark Information

Trademarks of the GlaxoSmithKline group of companies
ANORO ELLIPTA
ARNUITY ELLIPTA
INCRUSE ELLIPTA
RELVAR ELLIPTA
SERETIDE DISKUS
BREO ELLIPTA
SERETIDE ACCUHALER

Trademarks not owned by the GlaxoSmithKline group of companies
SAS
Seebri Breezhaler
Spiriva HandiHaler
Symbicort Turbuhaler
Symbicort Turbohaler
Ultibro Breezhaler

12.2. Appendix 2: Inhaler Specific Errors for the inhalers used in the study

There are no universally agreed checklists that define critical errors and over all errors for specific inhalers. The checklist and critical errors, for use in this study have been developed by GSK for each inhaler based upon:

- A review of the patient information leaflet for each inhaler and the steps defined therein for correct use
- The available literature which is exhaustive for a number of the commonly used inhalers
- Review of these errors with a group of external inhaler experts

The critical errors checklist are, therefore, as robust as possible. Furthermore, GSK has used selected sites with trained assessors to ensure as much consistency as possible in the valuation of errors in study subjects.

Checklist of instructions for correct use will be based on the steps listed in the patient information leaflets/package insert for each device. Some of the steps outlined in the patient information leaflets/package inserts require several actions to be identified and checked by the HCP.

Critical Errors are identified in **bold text** in the list below. A critical error is defined as an error that is most likely to result in no or significantly reduced medication being inhaled.

These errors will be captured in a checklist provided for HCP assessment of DPI use.

DISKUS/ACCUHALER
Failed to open cover
Lever is not pushed back
Shook the device after dose preparation
No exhalation before an inhalation
Exhaled directly into mouthpiece
No seal by the lips round the mouthpiece during the inhalation
Inhalation manoeuvre: 
 - steady - deep
Did not hold breath
Did not close the device (Note: this is an error but one which does not affect the medication that is inhaled)
Any other comments: [free text box]

ELLIPTA
Failed to open cover
Shook the device after dose preparation
No exhalation before an inhalation
Exhaled directly into mouthpiece
No seal by the lips round the mouthpiece during the inhalation
Inhalation manoeuvre: 
 - long - steady - deep
Blocked air inlet during inhalation manoeuvre
Did not hold breath
Did not close the device (Note: this is an error but one which does not affect the medication that is inhaled)
Any other comments: [free text box]

TURBUHALER
Failed to remove cap
Did not hold device upright ($\pm 45\%$ OK) during dose preparation
Base not twisted fully backwards and forwards, no click heard
Device tipped downwards after dose preparation
Shook the device after dose preparation
No exhalation before an inhalation
Exhaled directly into mouthpiece
No seal by the lips round the mouthpiece during the inhalation
Inhalation manoeuvre: 
 - forceful - deep 
Note to HCP: it is important that the inhalation is forceful and deep from the start for this inhaler

Blocked air inlet during inhalation manoeuvre
Did not hold breath
Did not close the device (Note: this is an error but one which does not affect the medication that is inhaled)
Any other comments: [free text box]

HANDIHALER
Failed to remove capsule
Failed to insert capsule into the chamber
Did not completely close device capsule chamber (heard click when satisfactory)
Did not pierce the capsule (HCP should check capsule was pierced)
Shook the device after dose preparation
No exhalation before an inhalation
Exhaled directly into mouthpiece
No seal by the lips round the mouthpiece during the inhalation
Inhalation manoeuvre: 
- slow- deep
Capsule did not rattle
Blocked air inlet during inhalation manoeuvre
Did not hold breath
Did not check inside the capsule chamber if powder was left / did not make a second inhalation
Any other comments: [free text box]

12.3. Appendix 3: Inhaler Preference Questionnaires

Inhaler Preference Questionnaire Version 1

Instructions: Please complete the following questions related to the treatments you used during this study. Check only one response for each question.

1. Which treatment do you prefer based on the number of steps needed to take your COPD medication?
 - DISKUS and HandiHaler
 - ELLIPTA
 - No preference

2. Which treatment do you prefer for taking your COPD medication?
 - DISKUS and HandiHaler
 - ELLIPTA
 - No preference

Inhaler Preference Questionnaire Version 2

Instructions: Please complete the following questions related to the treatments you used during this study. Check only one response for each question.

1. Which treatment do you prefer based on the number of steps needed to take your COPD medication?
 - ELLIPTA
 - DISKUS and HandiHaler
 - No preference

2. Which treatment do you prefer for taking your COPD medication?
 - ELLIPTA
 - DISKUS and HandiHaler
 - No preference

Inhaler Preference Questionnaire Version 3

Instructions: Please complete the following questions related to the treatments you used during this study. Check only one response for each question.

1. Which treatment do you prefer based on the number of steps needed to take your COPD medication?
 - Turbuhaler and HandiHaler
 - ELLIPTA
 - No preference

2. Which treatment do you prefer for taking your COPD medication?
 - Turbuhaler and HandiHaler
 - ELLIPTA
 - No preference

Inhaler Preference Questionnaire Version 4

Instructions: Please complete the following questions related to the treatments you used during this study. Check only one response for each question.

1. Which treatment do you prefer based on the number of steps needed to take your COPD medication?
 - ELLIPTA
 - DISKUS and HandiHaler
 - No preference

2. Which treatment do you prefer for taking your COPD medication?
 - ELLIPTA
 - DISKUS and HandiHaler
 - No preference

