Currently, subjects requiring triple therapy can be prescribed ICS/LABA and LAMA in separate inhalers. The specific ICS/LABA and LAMA prescribed determine whether the inhaler types (and thereby the inhalation techniques) and the dosing regimens are similar or different. Use of different inhaler types with different inhalation techniques and dosing regimens can add to treatment complexity, and also increase the potential for errors in inhaler use that reduce or preclude drug delivery to the site of action in the lungs [Cochrane, 2000, Van der Palen, 1999]. Fixed-dose combination inhalers that minimise the number of inhalers required would simplify treatment, improve adherence, reduce errors in inhaler use, and potentially lead to better outcomes [GOLD 2016].

The skill and ability of the COPD patient to use the prescribed inhaler/s correctly coupled with adequate training in inhaler technique are also critical to ensure effective drug delivery [Cochrane, 2000, Melani, 2011]. For any prescribed inhaler, the patient needs to follow all the steps in the patient leaflet correctly in order to ensure optimal drug delivery. In this regard, the time needed for a primary care nurse or physician, or a community pharmacist to train a patient in correct use of an inhaler at the time of initial prescription, and for any subsequent retraining becomes important. Given the time demands on healthcare professionals, a device which is simple to use and requires minimal time to train would be desirable [Bonini, 2015]. Further, patients may prefer easy-to-use inhalers having fewer steps to deliver drug; this has the potential to improve compliance and thereby impact outcomes.

ELLIPTA DPI has been designed to be simple for patients to use. In COPD patients' naïve to Ellipta and comparator inhalers, data has shown that patients make fewer critical and overall errors when using ELLIPTA as compared to other common DPIs tested [Van Der Palen, 2016(a)]. ELLIPTA DPI was also shown to be preferred by patients for a number of attributes, including number of steps and training time required to receive therapy [Van Der Palen, 2016(b), Van Der Palen, 2016(c), Komase, 2014]. ELLIPTA is already available to deliver a LABA/ICS combination (BREO ELLIPTA), LAMA

(INCRUSE ELLIPTA), and LAMA/LABA combination (ANORO ELLIPTA). Closed triple therapy (ICS/LAMA/LABA) is currently being assessed in clinical studies to deliver all 3 active treatments from a single ELLIPTA DPI.

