7.3. Blinding

This is an open-label study; however, the order of treatment and preference questionnaire answered by a participant will be assigned using an IWRS. The site will contact the IWRS prior to study treatment administration for each participant. The site will record the treatment assignment on the applicable case report form, if required. Potential bias will be reduced by randomising the order of treatment and the preference questionnaire version answered by subjects.

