9.1.1. Assessment of Errors in Use of Device

Within each sub-study, subjects will be randomised for the order of treatment. One treatment will require subjects to demonstrate use of a single inhaler (ELLIPTA), while the other treatment will require the subject to demonstrate use of 2 inhalers (DISKUS-HandiHaler in Sub Study 1 or Turbuhaler-HandiHaler in Sub Study 2).

Subjects will be provided with the relevant section of the PIL, explaining correct use, for each inhaler they are to be tested on. The critical and over all errors per inhaler and how these have been defined are included in Appendix 2.

The errors listed will be in aligned with the correct use information from the respective PILs, in a checklist for each inhaler and these will be provided to HCPs for scoring errors during the study conduct. The checklists will be provided in the Study Reference Manual.

Figure 2 depicts the process flow for assessing inhaler use errors and further details are provided, for each treatment, in Section 9.1.1.1 and Section 9.1.1.2.

Figure 2 Assessment of errors in use for each DPI tested**9.1.1.1. Assessment of ELLIPTA error in use**

Subject will be asked to read the patient instruction leaflet for ELLIPTA and then demonstrate ELLIPTA use. Any errors (critical or non-critical) made by the subject while using the ELLIPTA will be recorded by the HCP on the checklist provided. If the subject makes no errors, this will also be recorded by the HCP, and there will be no further assessments. If the subject makes any error in the use of the ELLIPTA, the HCP will provide instruction in the correct use of the ELLIPTA to the subject. The subject will then demonstrate ELLIPTA use again. If the subject makes no errors, this will be recorded by the HCP and there will be no further assessments. If the subject again makes errors in the use of the ELLIPTA any errors will be recorded by the HCP. The HCP will again provide instruction in the correct use for the final time, following which the subject will then demonstrate ELLIPTA use one final time. Any errors made during this demonstration will be recorded. There will be no further assessments. In total, the HCP can provide instruction in the use of the inhaler up to two times.

9.1.1.2. Assessment of DISKUS-HandiHaler in Sub Study 1, or Turbuhaler-HandiHaler in Sub Study 2, for error in use

Subjects will be provided with 2 inhalers and 2 PILs dependent on which sub study they are included in.

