9.1.2. Assessments of Preference

After completing the errors in use assessment for both treatments, the HCP will ask the subject questions from the assigned preference questionnaire. The wording of the questionnaires is included in Appendix 3.

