8.1.2.5. Preference attributes

Secondary Statistical Analyses
Endpoint(s)

 • Treatment preference from questionnaire for number of steps required to take medication • Treatment preference from questionnaire preferred treatment for overall treatment preference.
Model Specification

 • The endpoint of treatment preference will be analysed using the Intent-to-treat population. • This endpoint will be analysed using the Cochran-Mantel-Haenszel test.
Model Checking & Diagnostics

 • Refer to Appendix 9: Model Checking and Diagnostics for Statistical Analyses.
Model Results Presentation

 • The percentage of preference for each specific attribute (i.e., preferring ELLIPTA inhaler, preferring the other inhaler, and no preference) will be summarised by inhaler use sequence. • Subject preference will also be analysed using a Cochran-Mantel-Haenszel test. The Cochran-Mantel-Haenszel test serves as a stratified approximation to Prescott's test, a variation of a one-sample chi-square test that accounts for study inhaler sequence and subjects who indicate no preference. P-values from this analysis will be presented in summary and analysis tables.
SAS Code

 • SAS code for stratified approximation to Prescott's test for each preference question: <pre>ods output CMH = cmhi (where = (upcase(AltHypothesis) = 'ROW MEAN SCORES') keep = AltHypothesis Prob) ; proc freq data = pref_data ; tables seq * pref_ord country / cmh ; run ;</pre> 
Country will be included in the model providing there are sufficient subjects distributed to enable the model to run. If the model will not run with country in the model then country will be removed from the model.
 
pref_ord is derived as shown in Section 11.5.4

9. OTHER STATISTICAL ANALYSES**9.1. Efficacy Analyses****9.1.1. Overview of Planned Other Efficacy Analyses**

The other efficacy analyses will be based on the Intent-to-treat population, unless otherwise specified.

[Table 5](#) provides an overview of the planned other efficacy analyses, with further details of data displays being presented in [Appendix 11: List of Data Displays](#).

Table 5 Overview of Planned Other Efficacy Analyses

	Absolute			
	Stats Analysis	Summary		Individual
	T	T	F	L
Number of critical errors made after Healthcare Professional (HCP) instructions				

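### All four preference questionnaires ask about number of steps before overall preference, so any influence of the first answer on the second could not be told apart from a device preference

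*Protocol*

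**What the plan says.** Protocol Appendix 3 gives four questionnaire versions, each with two questions. Question 1 is always "Which treatment do you prefer based on the number of steps needed to take your COPD medication" and question 2 is always "Which treatment do you prefer for taking your COPD medication". Versions 1 and 3 list the two-inhaler combination as the first answer option; Versions 2 and 4 list ELLIPTA first.

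Protocol 7.3 treats this arrangement as a safeguard in an open-label study: "Potential bias will be reduced by randomising the order of treatment and the preference questionnaire version answered by subjects". Protocol 9.1.2 places the questionnaire after both treatments have been assessed, when "the HCP will ask the subject questions from the assigned preference questionnaire".

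Both preference items are secondary endpoints (Protocol 4; SAP 1), and each gets a p-value (SAP 8.1.2.5 and shell EFF_T03). The test is a Cochran-Mantel-Haenszel approximation to Prescott's test, described as "a variation of a one-sample chi-square test that accounts for study inhaler sequence and subjects who indicate no preference". Country may be added if the data allow. Question order is not mentioned.

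On the attribute in question 1, Protocol 3.2 states that "ELLIPTA DPI was also shown to be preferred by patients for a number of attributes, including number of steps" and that "patients may prefer easy-to-use inhalers having fewer steps to deliver drug".

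**The concern.** Question 1 asks every subject to commit to a choice on one attribute immediately before giving the overall judgement. The protocol's own background names that attribute as one on which ELLIPTA is expected to do well. If the first answer pulls on the second, the pull would plausibly be towards ELLIPTA, whichever device was used first and whichever answer option was printed first.

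The existing randomisation does not address this. Treatment order deals with period effects, and questionnaire version deals with the position of the answer options. Because question order is constant, no analysis of the collected data could estimate or remove its effect. At stake are the p-value and the reported percentage for overall preference.

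**Working it through.** **Question order.** Steps come first and overall preference second in 4 of 4 versions; 0 of 4 are reversed. The versions differ only in option order and in the comparator named.

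**Direction of any influence.** Protocol 9.1.1 sets one device against two: "One treatment will require subjects to demonstrate use of a single inhaler (ELLIPTA), while the other treatment will require the subject to demonstrate use of" two. As a rough proxy for steps, I counted the checklist items in Protocol Appendix 2, leaving out the free-text box:

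- ELLIPTA: 9
- DISKUS + HandiHaler: 9 + 13 = 22
- Turbuhaler + HandiHaler: 12 + 13 = 25

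With the statements in Protocol 3.2, this makes number of steps an attribute likely to favour ELLIPTA in both sub-studies.

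**How the planned test would read a one-way shift.** Under SAP 11.5.4, a preference for ELLIPTA scores pref_ord = −1 when ELLIPTA came first and +1 when it came second. Let δ be the proportion choosing ELLIPTA minus the proportion choosing the combination, and p₀ the proportion with no preference. The expected mean score is −δ in one order and +δ in the other, so the sequence contrast is 2δ whether δ comes from true preference or from question order. With n subjects split equally, the row-mean-score statistic is approximately

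(2δ)² / [(1 − p₀) × 4/n] = nδ² / (1 − p₀).

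**Illustration.** The documents give no shift size, so there is no plan figure to reproduce and a range is assumed. Inputs are n = 72 per sub-study (Protocol 5.2), 36 per treatment order, two-sided 5%, and no true preference. Two definitions of the shift were simulated:

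- Scale A: start from 45% ELLIPTA, 45% combination, 10% no preference, and move 5, 10 or 15 percentage points of the sample straight from combination to ELLIPTA (100,000 trials each).
- Scale B: start from 40%, 40%, 20%, and move 5%, 10%, 15% or 20% of all non-ELLIPTA answers to ELLIPTA (20,000 trials each).

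| Scenario | ELLIPTA / none / combination | δ | 72δ²/(1 − p₀) | Simulated rejection |
|---|---|---|---|---|
| A, no shift | 45 / 10 / 45 | 0 | 0 | 5.1% |
| A, 5 points | 50 / 10 / 40 | 0.10 | 0.80 | 14.3% |
| A, 10 points | 55 / 10 / 35 | 0.20 | 3.20 | 43.2% |
| A, 15 points | 60 / 10 / 30 | 0.30 | 7.20 | 77.6% |
| B, no shift | 40 / 20 / 40 | 0 | 0 | 4.9% |
| B, 5% | 43 / 19 / 38 | 0.05 | 0.22 | 7.3% |
| B, 10% | 46 / 18 / 36 | 0.10 | 0.88 | 15.4% |
| B, 15% | 49 / 17 / 34 | 0.15 | 1.95 | 28.3% |
| B, 20% | 52 / 16 / 32 | 0.20 | 3.43 | 46.1% |

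Hand check of one row by the normal approximation: √0.80 = 0.894, and Φ(0.894 − 1.96) + Φ(−0.894 − 1.96) = 0.145, against 14.3% simulated. With 20% no preference, Scale A gives slightly higher figures (15.4%, 47.7%, 82.7%).

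The scales differ mainly in how much net difference a given step creates. At δ = 0.10 they give 14% and 15%; at δ = 0.20, 43% and 46%.

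**The case against.** The strongest reply is that the documents do not show the bias. No section says that the steps question changes the overall answer, in which direction, or by how much. That patients may prefer fewer steps makes steps a legitimate part of overall preference; it is not evidence that asking about them distorts it. Subjects will also just have read one leaflet against two and handled one inhaler against two, so one more question may add little. This stands, and it limits the point to a risk of bias.

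The assumed shifts are not small. On Scale A, 5, 10 and 15 points mean that 5/45 = 11%, 10/45 = 22% and 15/45 = 33% of those preferring the combination reverse outright, with none stopping at no preference. The no-preference starting point also fits poorly with a protocol that reports earlier preference for ELLIPTA. This too stands: the rejection rates illustrate a mechanism and do not estimate this trial's error rate.

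Mode of administration is unclear. Protocol 9.1.2 has the healthcare professional ask the questions, while the Schedule of Activities has the subject complete the form and Appendix 3 tells the subject to tick one response. If both questions are in view together, strict sequence matters less, and reversing it is less certain to help.

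A reader might infer that the overall-preference result is biased towards ELLIPTA, or that its false-positive rate is 43% or 78%. The documents support neither. They establish only that the order is fixed and that the planned analysis could not detect an effect of it.

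**Conclusion.** The point holds as a cheap improvement to a secondary endpoint. Question order is the same in every version, the attribute asked first is one the protocol expects to favour ELLIPTA, and any resulting one-way shift would enter the planned test as a device preference.

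The size is unknown. If there were no true preference, rejection would rise from 5% to 7% or 14% at the smallest assumed step and to 28% or 78% at the third, depending on the scale. If true preference for ELLIPTA is strong, the test's conclusion may not change, although the reported percentage could still be inflated. The primary endpoint, the sample size and the error analyses are untouched.

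**What to change.** In all four versions, ask overall preference first and number of steps second, keeping the randomised option order. Alternatively, cross question order with option order in the randomised versions, which also allows an order effect to be examined. State whether the form is read out or self-completed.

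In the SAP, change the order of the two questions in shell EFF_T03, which prints the question text without numbers, and swap the Question 1 and Question 2 definitions in the preference-listing footnote.

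The simple reversal costs form and eCRF relabelling, with no added subjects, visits or analyses; counterbalancing also needs further versions in the randomisation schedule. The downsides are possible carry-over from the overall answer into the steps item, itself a secondary endpoint, and possible loss of comparability with earlier forms. Protocol 5.4 says the design was used before, in studies of errors and/or preference, but not whether the same questionnaire was used.

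If data have already been collected, report the fixed question order as a limitation of the overall-preference result.

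In the same edit, correct Version 4. Protocol Table 2 assigns it to sequences F and G of Sub-study 2, two of its four equally allocated sequences, yet its combination option names DISKUS and HandiHaler, where Version 3 names Turbuhaler and HandiHaler.

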Treatment Groups and Duration: Duration is a single visit and subjects are randomised to receive treatments below; dependent on which sub-study they are included in.

There is no active treatment and subjects will continue to take their own prescribed COPD medication for the duration of the study.

Sub Study 1 Treatment Sequences

Sequence	Period 1	Period 2	Preference Questionnaire
A	ELLIPTA	DISKUS + HandiHaler	1
B	DISKUS + HandiHaler	ELLIPTA	2
C	ELLIPTA	DISKUS + HandiHaler	2
D	DISKUS + HandiHaler	ELLIPTA	1

Sub Study 2 Treatment Sequence

Sequence	Period 1	Period 2	Preference Questionnaire
E	ELLIPTA	Turbuhaler + HandiHaler	3
F	Turbuhaler + HandiHaler	ELLIPTA	4
G	ELLIPTA	Turbuhaler + HandiHaler	4
H	Turbuhaler + HandiHaler	ELLIPTA	3

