7.2. Method of Treatment Assignment

All participants will be centrally randomized using an Interactive Web Response System (IWRS). Before the study is initiated, the log in information & directions for the IWRS will be provided to each site.

Participants will be assigned in equal numbers to one of four sequences for the sub-study they are included on, in accordance with the randomization schedule generated by Clinical Statistics, prior to the start of the study and using validated internal software.

The possible sequences for each sub study are shown in Table 1 and Table 2

Table 1 Sub Study 1 Treatment Sequences

Sequence	Period 1	Period 2	Preference Questionnaire
A	ELLIPTA	DISKUS + HandiHaler	1
B	DISKUS + HandiHaler	ELLIPTA	2
C	ELLIPTA	DISKUS + HandiHaler	2
D	DISKUS + HandiHaler	ELLIPTA	1

Table 2 Sub Study 2 Treatment Sequence

Sequence	Period 1	Period 2	Preference Questionnaire
E	ELLIPTA	Turbuhaler + HandiHaler	3
F	Turbuhaler + HandiHaler	ELLIPTA	4
G	ELLIPTA	Turbuhaler + HandiHaler	4
H	Turbuhaler + HandiHaler	ELLIPTA	3

Study treatments will be dispensed at the study visit summarized in SOA

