	Sub-study 2 Treatment Sequence			
	Sequence	Period 1	Period 2	Preference Questionnaire
	E	ELLIPTA	Turbuhaler + HandiHaler	3
	F	Turbuhaler + HandiHaler	ELLIPTA	4
	G	ELLIPTA	Turbuhaler + HandiHaler	4
	H	Turbuhaler + HandiHaler	ELLIPTA	3

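### Preference Questionnaire Version 4 names DISKUS instead of Turbuhaler, so half of Sub-study 2 has no box for the comparator it tested

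*Protocol*

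**What the plan says.** Protocol 5.1 defines Sub-study 2 as ELLIPTA against Turbuhaler plus HandiHaler. Three tables give sequences F and G Questionnaire 4: the Protocol Synopsis ("Sub Study 2 Treatment Sequence"), Protocol 7.2 ("Table 2 Sub Study 2 Treatment Sequence") and SAP 2.3 ("Sub-study 2 Treatment Sequence").

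Protocol 9.1.2 makes the appendix the source of the text: "The wording of the questionnaires is included in Appendix 3". There, under "Inhaler Preference Questionnaire Version 4", the comparator option in both questions is "DISKUS and HandiHaler". The same phrase is correct in Versions 1 and 2, which belong to Sub-study 1; the error is in Version 4 only. The form's own instruction reads "Please complete the following questions related to the treatments you used during this study", and it allows one answer per question.

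Protocol 10.4.1 and SAP 8.1.2.5 analyse both preference items as secondary endpoints with a Cochran-Mantel-Haenszel (CMH) test. The SAP does not reprint or correct the forms.

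**The concern.** DISKUS is not tested in Sub-study 2. A subject on sequence F or G who prefers Turbuhaler plus HandiHaler must tick a pair not used in the trial, tick ELLIPTA, or declare no preference. The missing option is always the comparator's, so any answer that moves elsewhere shifts the result towards ELLIPTA. Version 4 is used in both device orders, so adjusting for sequence does not remove the shift. The preference listing and table would reveal a DISKUS tick, but not a comparator preference recorded as ELLIPTA or no preference. That information cannot be recovered afterwards.

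**Working it through.** **Comparing the forms**

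| Version | Sub-study | Options as printed, in order |
|---|---|---|
| 1 | 1 | DISKUS pair, ELLIPTA, none |
| 2 | 1 | ELLIPTA, DISKUS pair, none |
| 3 | 2 | Turbuhaler pair, ELLIPTA, none |
| 4 | 2 | ELLIPTA, DISKUS pair, none |

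Versions 1 and 2 are the same form with the first two options swapped. Versions 3 and 4 should be the same kind of pair, but Version 4 carries Version 2's options. The error is in both questions, so it is not a stray extraction fault.

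**Subjects affected.** Allocation is equal over four sequences (Protocol 7.2), with up to 80 randomised and 72 evaluable (Protocol 10.2). 2/4 × 80 = 40 and 2/4 × 72 = 36. F and G have opposite device orders, so half of each order group is affected.

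**Effect on the planned test.** The documents give no expected preference split, so the splits (ELLIPTA/comparator/none) and answering patterns below are assumptions. The test is the CMH row-mean-score test of pref_ord (−1, 0, 1, coded as in SAP 11.5.4) by device order. It has no country term and 18 subjects per sequence. The statistic is Q = (N − 1)r², referred to chi-square on 1 df at two-sided 5%, where r is the correlation between device order and pref_ord. Only answers in F and G are altered.

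Example: a true tie at 45/45/10, with half of the comparator-preferrers on Version 4 moving to no preference.

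- Version 4 split: 45 / 22.5 / 32.5. Averaged with Version 3 (45/45/10): 45 / 33.75 / 21.25.
- Mean pref_ord is ±(45 − 33.75)/100 = ±0.1125 in the two orders. Its mean square is 0.45 + 0.3375 = 0.7875.
- r² = 0.1125²/0.7875 = 0.0161, and 71 × 0.0161 = 1.14, with square root 1.07.
- Approximate rejection rate: P(Z > 1.96 − 1.07) + P(Z < −1.96 − 1.07) ≈ 0.19.

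Exact enumeration gives 0.185 for this case. The full set at the 45/45/10 tie, exact except for the two 10% rows, which are simulated:

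| Comparator-preferrers on Version 4 | False-positive rate |
|---|---|
| All tick DISKUS, counted as comparator | 5.0% |
| 10% / 25% / 50% / 100% move to no preference | about 5.5% / 8% / 19% / 66% |
| 10% / 25% / 50% move to ELLIPTA | about 7% / 17% / 52% |
| All tick DISKUS, and only those ticks are set to missing | 65% |
| All Version 4 answers left out (n = 36) | 4.8% |

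Power when all Version 4 answers are left out, against a correct form:

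| True split | n = 72 | n = 36 |
|---|---|---|
| 55/35/10 | 43% | 24% |
| 60/30/10 | 78% | 48% |
| 65/25/10 | 96% | 74% |

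Independent simulation agrees with the exact figures to within 0.004.

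**The case against.** The strongest reply is that the SAP already copes. SAP 11.5.4 is not split by sub-study and gives either two-inhaler pair the same comparator code. Applied literally, a DISKUS tick in Sub-study 2 counts as the comparator, which is the harmless 5.0% row. That is a fair reading, although the rule was probably not written for this case. It does nothing for subjects who tick ELLIPTA or no preference. A DISKUS tick is also not unambiguous: exclusion criterion 4 bars recent DISKUS experience only in Sub-study 1, so some Sub-study 2 subjects may know that inhaler.

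Large shifts may also be unlikely. The subject has just handled both treatments, only one two-inhaler option is shown, and "the HCP will ask the subject questions from the assigned preference questionnaire". This makes the extreme rows less plausible, and a 10% shift does little. It is still no reliable safeguard: the Schedule of Activities says the subject completes the form, and staff who notice the wrong name have no instruction on what to do.

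Finally, Protocol 3.2 reports that ELLIPTA was preferred in earlier data. If the true split were as strong as 80/10/10, half moving to no preference would change the average report only to 80/7.5/12.5, with power near 100% either way. The conclusion would then survive. At 55/35/10, however, the same shift raises the rejection rate from 43% to 79%, so the distortion is not confined to an exact tie.

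**Conclusion.** The concern holds. Version 4 as printed contradicts the treatment tables and its own instruction, and nothing in either document corrects it. Both secondary preference endpoints of Sub-study 2 are compromised for half of its subjects; the primary endpoint, its power and all of Sub-study 1 are not. The statistical harm ranges from almost none to severe, depending on answering behaviour that the documents do not address. Whether the forms at sites carry the same misprint cannot be seen from the documents. It must be fixed because the form cannot correctly record the outcome it is meant to measure, any bias from moved answers favours ELLIPTA, and the loss cannot be undone. The case does not rest on the most extreme rows of the table.

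**What to change.** Amend Protocol Appendix 3, Version 4, questions 1 and 2, so that the comparator option names Turbuhaler and HandiHaler. Check the site forms and the eCRF against the corrected text before Sub-study 2 starts. Done then, this has no statistical cost and needs no SAP change.

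If any answers were collected on the misprinted form, state before database freeze that Sub-study 2 preference results will be reported by questionnaire version. Add an analysis that leaves out every answer from that form. Do not set only the DISKUS ticks to missing, since that removes comparator preferences alone (the 65% row). The added analysis has the lower power shown above. Its remaining subjects (E and H) still cover both device orders, but all of them saw the Turbuhaler pair listed first, so the balance of option order intended in Protocol 7.3 is lost.
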